5 STUDY DESIGN

5.1 Overall Design

[figure not shown]
This will be a Phase 3b/4, open-label, study of first-line combination therapy (nivolumab/ipilimumab) in participants with previously untreated, advanced or metastatic RCC. Participants will be assigned to 1 of the 4 cohorts (Figure 5.1-1).

Treatment in all cohorts will continue until progression, unacceptable toxicity, withdrawal of consent, or end of trial. Treatment period will last for up to 2 years. The study will continue until the last enrolled participant completes 5 years of survival follow up from LPFT. Participants will be permitted to continue treatment beyond PD (RECIST 1.1) under protocol-defined circumstances (See Section 7.9). No dose increases or reductions will be allowed for nivolumab or ipilimumab.

Participants in any cohort, who discontinue combination therapy early due to an adverse event, may be eligible to receive nivolumab monotherapy (480 mg every 4 weeks), contingent upon discussion with, and approval by the Medical Monitor.

- The study design schematic is presented in Figure 5.1-1.

Figure 5.1-1: Study Design Schematic

Abbreviations: ccRCC, clear-cell renal cell carcinoma, KPS, Karnofsky performance score; RCC, renal cell carcinoma; Q, every.

Note: All participant numbers above are approximate. Enrollment of participants with a favorable risk score per IMDC Prognostic Criteria will be capped at 25% of Cohort 1. If the number of participants in Cohorts 3 and 4 cannot be reached, the number of patients enrolled in the clear-cell or non-clear cell cohorts may be increased.

Nivolumab maintenance in Cohort 2-4 to begin 6 weeks after last combination dose.

*The study will continue until the last enrolled participant completes 5 years of follow up from LPFT. The treatment period duration is a maximum of 2 years. Participants will be permitted to continue treatment beyond PD (RECIST 1.1) under protocol defined circumstances (if investigator-assessed clinical benefit is achieved, treatment is well-tolerated, and participant has stable PS, etc.)

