7.4.1 Study Treatment Dose Delay Criteria

Study treatment administration should be delayed for the following:

- Grade 2 non-skin, drug-related adverse event, with the exception of fatigue
- Grade 2 drug-related creatinine, AST, ALT and/or Total Bilirubin abnormalities
- Grade 3 skin, drug-related adverse event
- Grade 3 drug-related laboratory abnormality, with the following exceptions:
 - Grade 3 lymphopenia or asymptomatic amylase or lipase does not require dose delay
 - Grade ≥ 3 AST, ALT, Total Bilirubin will require dose discontinuation (see [Section 8.1.1](#))
- Any adverse event, laboratory abnormality, or intercurrent illness which, in the judgment of the investigator, warrants delaying the dose of study medication.

Participants who require delay of study treatment should be re-evaluated weekly or more frequently if clinically indicated and resume nivolumab dosing when re-treatment criteria are met.

During Cycles 1 and 2, both nivolumab and ipilimumab must be delayed at the same time.

Because of the potential for clinically meaningful nivolumab or ipilimumab-related AEs requiring early recognition and prompt intervention, management algorithms have been developed for

suspected pulmonary toxicity, GI, hepatotoxicity, endocrinopathy, skin toxicity, neurological toxicity and renal toxicity.

In order to standardize the management of overlapping adverse event management algorithms present in both the BMS-936558 (nivolumab) and ipilimumab IB (**GI, hepatic, and endocrine** algorithms), the recommendations are to follow the BMS-936558 (nivolumab) IB adverse event algorithms as opposed to the ipilimumab IB algorithms.

The algorithms recommended for utilization in are included in [Appendix 8](#).

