 - Grade 4 drug-related endocrinopathy adverse events, such as, hyper- or hypothyroidism, or glucose intolerance, which resolve or are adequately controlled with physiologic hormone replacement (corticosteroids, thyroid hormones) or glucose-controlling agents, respectively, may not require discontinuation after discussion with and approval from the BMS Medical Monitor.

- Any event that leads to delay in dosing lasting > 8 weeks during Cycle 1- 2, and >10 weeks in cycle 3 or later for Cohorts 2-4, and >10 weeks for Cohort 1, from the previous dose requires discontinuation, with the following exceptions:
 - Dosing delays to allow for prolonged steroid tapers to manage drug-related adverse events are allowed.
 - Dosing delays lasting longer than the number of weeks allowed for the respective cohorts that occur for non-drug-related reasons may be allowed if approved by the BMS medical monitor.

Prior to re-initiating treatment in a participant with a dosing delay lasting > 8 weeks for Cohorts 2 through 4, or >10 weeks for Cohort 1, the BMS medical monitor must be consulted and provide written approval for participants with expected clinical benefit as per investigator assessment. Tumor assessments should continue as per protocol even if dosing is delayed. Periodic study visits to assess safety and laboratory studies should also continue every 6 weeks or more frequently if clinically indicated during such dosing delays.

Any adverse event, laboratory abnormality, or intercurrent illness which, in the judgment of the Investigator, presents a substantial clinical risk to the participant with continued nivolumab dosing.

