8.1.2 Criteria to Resume Treatment

Missed doses of nivolumab and/or ipilimumab should be administered as soon as the participant meets criteria to resume treatment. If a dose has been missed, the participant should not wait until the next scheduled dosing date.

Participants may resume treatment with study drug when the drug-related AE(s) resolve to Grade ≤ 1 or baseline value, with the following exceptions:

- Participants may resume treatment in the presence of Grade 2 fatigue
- Participants who have not experienced a Grade 3 drug-related skin AE may resume treatment in the presence of Grade 2 skin toxicity
- For participants with Grade 2 AST, ALT and/or Total Bilirubin Abnormalities, dosing may resume when laboratory values return to baseline and management with corticosteroids, if needed, is complete.
- Participants with combined Grade 2 AST/ALT AND total bilirubin values meeting discontinuation parameters ([Section 8.1.1](#)) should have treatment permanently discontinued.
- Drug-related pulmonary toxicity, diarrhea or colitis must have resolved to baseline before treatment is resumed. Participants with persistent Grade 1 pneumonitis after completion of a steroid taper over at least 1 month may be eligible for retreatment if discussed with and approved by BMS Medical Monitor.
- Participants with drug-related endocrinopathies adequately controlled with only physiologic hormone replacement may resume treatment after consultation with the BMS Medical Monitor.
- Adrenal insufficiency requires discontinuation regardless of control with hormone replacement.

If treatment is delayed > 8weeks for Cohorts 2 through 4, or >10 weeks for Cohort 1, the participant must be permanently discontinued from study therapy, except as specified in [Section 8.1.1](#).

For participants in Cohort 1, during Cycles 1 and 2, both nivolumab and ipilimumab must be resumed on the same day. For participants in Cohort 2 to 4, all four doses of nivolumab combined with ipilimumab must be given prior to beginning nivolumab monotherapy (Cycle 3 and beyond). Participants in any cohort, who discontinue combination therapy early due to an adverse event, may be eligible to receive nivolumab monotherapy (480 mg every 4 weeks), contingent upon discussion with, and approval by the Medical Monitor.

If the participant is unable to receive either combination therapy or nivolumab monotherapy permanent discontinuation is required.

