2 STUDY DESCRIPTION

2.1 Study Design

This is a Phase 3b/4, open-label study of first-line combination therapy (nivolumab/ ipilimumab) in participants with previously untreated, advanced or metastatic RCC. Participants will be assigned to 1 of the 4 cohorts.

Participants in Cohort 1 should receive nivolumab at a dose of 6 mg/kg as about a 60-minute IV infusion, and ipilimumab at a dose of 1 mg/kg as about an 30-minute IV infusion on Day 1 Week 1 of each cycle (every 8 weeks), until progression, unacceptable toxicity, withdrawal of consent, the study ends or up to a maximum of 24 month whichever occurs first. Participants should begin study treatment within 5 calendar days of treatment assignment. Beginning on Day 1 of Week 5 of Cycle 1, participants will receive nivolumab 480 mg flat dose, as a 60-minute infusion, and then again every 8 weeks until progression, unacceptable toxicity, withdrawal of consent, the study ends or up to a maximum of 24 month whichever occurs first.

Participants in Cohorts 2, 3, and 4, will receive nivolumab at a dose of 3 mg/kg as a 60-minute infusion, and ipilimumab at a dose of 1 mg/kg as a 30-minute infusion on Day 1 Week 1 and Day 1 Week 4 of each cycle (every 6 weeks) until for up to 4 doses (2 cycles). Participants should begin study treatment within 5 calendar days of treatment assignment. Beginning with Cycle 3 (6 weeks \pm 3 days from last combo dose), participants in Cohorts 2, 3 and 4 will receive nivolumab at a dose of 480 mg as a 60-minute infusion every 4 week (\pm 3 days) until progression, unacceptable toxicity, withdrawal of consent, the study ends, or up to a maximum of 24 months, whichever occurs first.

[figure not shown]
The study will continue until the last enrolled participant completes 5 years of survival follow up from last patient first treatment (LPFT). Participants will be permitted to continue treatment beyond progressive disease (PD) (Response Evaluation Criteria in Solid Tumor (RECIST) 1.1) under protocol-defined circumstances (See Protocol Section 7.9). No dose increases or reductions will be allowed for nivolumab.

Participants in any cohort, who discontinue combination therapy early, may be eligible to receive nivolumab monotherapy (480 mg every 4 weeks), contingent upon discussion with, and approval by the Medical Monitor.

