7.4 Extent of Exposure

7.4.1 Administration of Study Therapy

The following parameters will be summarized (descriptive statistics) for all treated subjects, according to the general methods:

- Number of combined doses received (nivolumab + ipilimumab). A subject will be considered to have received combined doses of ipilimumab and nivolumab, if both infusions are administered on the same date.
- Number of doses received (nivolumab and ipilimumab)
- Cumulative dose (nivolumab and ipilimumab) in mg or mg/kg
- Relative dose intensity (%) using the following categories: < 50%; 50 - < 70%; 70 - < 90%; 90 - < 110%; ≥ 110%. (nivolumab and ipilimumab)

Table 7.4.1-1: Selection and Timing of Dose

Study Treatment	Unit Dose Strength(s)/Dosage Level(s)	Dosage Formulation Frequency of Administration	Route of Administration
Cohort 1	Nivolumab 6 mg/kg Ipilimumab 1 mg/kg Nivolumab 480 mg	Combination: D1W1 and then every 8 weeks. Monotherapy beginning D1W5 of C1, and then every 8 weeks	Nivolumab IV Ipilimumab IV
Cohort 2, 3, and 4	Nivolumab 3 mg/kg Ipilimumab 1 mg/kg Nivolumab 480 mg	Combination therapy: every 3 weeks for 4 doses. Maintenance monotherapy every 4 weeks afterwards.	Nivolumab IV Ipilimumab IV

Table 7.4.1-2: Study Therapy Parameter Definitions

	Cohort 1		Cohort 2, 3 and 4	
	Nivolumab	Ipilimumab 1 mg/kg	Nivolumab	Ipilimumab 1 mg/kg
Actual Dose (mg)	Actual dose is defined as the total dose delivered (mg) within each dosing visit.	Actual Dose (mg) is defined as the total dose delivered (mg) within each dosing visit.	Actual dose is defined as the total dose delivered (mg) within each dosing visit.	Actual Dose (mg) is defined as the total dose delivered (mg) within each dosing visit.
Actual Dose Level (mg/kg)	Actual Dose Level (mg/kg) is defined as the actual dose delivered (mg) within a dosing visit /most recent weight (kg) at the dosing visit.	Actual Dose Level (mg/kg) is defined as the actual dose delivered (mg) within a dosing visit /most recent weight (kg) at the dosing visit.	Actual Dose Level (mg/kg) is defined as the actual dose delivered (mg) within a dosing visit /most recent weight (kg) at the dosing visit.	Actual Dose Level (mg/kg) is defined as the actual dose delivered (mg) within a dosing visit /most recent weight (kg) at the dosing visit.

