Cumulative Dose (mg/Kg)	Cumulative Dose (mg/kg) is the sum of the actual dose levels administered to a subject during the study.	Cumulative Dose (mg/kg) is the sum of the actual dose levels administered to a subject during the study.	Cumulative Dose (mg/kg) is the sum of the actual dose levels administered to a subject during the study.	Cumulative Dose (mg/kg) is the sum of the actual dose levels administered to a subject during the study.
Cumulative Dose (mg)	Cumulative Dose (mg) is the sum of the actual doses administered to a subject during the study.	Cumulative Dose (mg) is the sum of the actual doses administered to a subject during the study.	Cumulative Dose (mg) is the sum of the actual doses administered to a subject during the study.	Cumulative Dose (mg) is the sum of the actual doses administered to a subject during the study.
Total Expected Dose (mg)	$[6 \times \text{Weight}^* \times (\text{Last dose date of } 6\text{mg/kg} - \text{Start dose date of } 6\text{mg/kg} + 56)/56]$ + $[480 \times (\text{Last dose date of } 480 \text{ mg} - \text{Start dose date of } 480 \text{ mg} + 56)/56]$ *Average weight during 6 mg/ kg dosing is used.	$[1 \times \text{Weight}^* \times (\text{Last dose date} - \text{Start dose date} + 56)/56]$ *Average weight during 1 mg/ kg dosing is used.	$[3 \times \text{Weight}^* \times (\text{Last dose date of } 6\text{mg/kg} - \text{Start dose date of } 6\text{mg/kg} + 21)/21]$ + $[480 \times (\text{Last dose date of } 480 \text{ mg} - \text{Start dose date of } 480 \text{ mg} + 28)/28]$ *Average weight during 3 mg/ kg dosing is used.	$[1 \times \text{Weight}^* \times (\text{Last dose date} - \text{Start dose date} + 21)/21]$ *Average weight during 1 mg/ kg dosing is used.

Table 7.4.1-2: Study Therapy Parameter Definitions

	Cohort 1		Cohort 2, 3 and 4	
	Nivolumab	Ipilimumab 1 mg/kg	Nivolumab	Ipilimumab 1 mg/kg
Relative Dose Intensity (%)	Cumulative Dose (mg) x100/ Total Expected Dose (mg)	Cumulative Dose (mg) x100/ Total Expected Dose (mg)	Cumulative Dose (mg) x100/ Total Expected Dose (mg)	Cumulative Dose (mg) x100/ Total Expected Dose (mg)
Duration of Treatment	Last dose date - Start dose date +1. Last dose date is the last date subject received Nivolumab 6 mg/kg or 480 mg.	Last dose date - Start dose date +1	Last dose date - Start dose date +1. Last dose date is the last date subject received Nivolumab 3 mg/kg or 480 mg.	Last dose date - Start dose date +1

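### Cohort 1 nivolumab relative dose intensity is overstated for undelayed participants who stop combination early and receive two or more 480 mg doses every 4 weeks

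*SAP*

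**What the plan says.** SAP Table 7.4.1-1 gives the planned Cohort 1 schedule: combination every 8 weeks, and for the 480 mg dose "Monotherapy beginning D1W5 of C1, and then every 8 weeks". In SAP Table 7.4.1-2 the expected nivolumab dose for Cohort 1 is the sum of a 6 mg/kg term and a 480 mg term. Each runs from its own first to its own last dose date with a 56-day divisor; the 480 mg term ends in "Start dose date of } 480 \text{ mg} + 56)/56". RDI is cumulative mg divided by expected mg, and SAP 7.4.1 reports "Relative dose intensity (%) using the following categories", of which the highest is 110% or more.

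The same SAP allows another schedule. Section 2.1 states: "Participants in any cohort, who discontinue combination therapy early, may be eligible to receive nivolumab monotherapy (480 mg every 4 weeks". Protocol 5.1 has the same provision for those "who discontinue combination therapy early due to an adverse event, may be eligible to receive nivolumab monotherapy (480 mg every 4 weeks", and protocol 8.1.2 repeats it: "may be eligible to receive nivolumab monotherapy (480 mg every 4 weeks), contingent upon discussion with, and approval by the Medical Monitor". The Cohort 1 cell of Table 7.4.1-2 has no term or exception for this 4-weekly phase. For Cohorts 2-4, where 480 mg is given every 4 weeks by design, the table uses a 28-day divisor.

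**The concern.** A Cohort 1 participant who moves to 480 mg every 4 weeks is scheduled for twice as many 480 mg doses per unit time as the formula expects. The numerator counts all of them; after the switch, the denominator counts about half. Someone dosed exactly on schedule would then appear to have had more than the intended dose and could fall in the 110%-or-more category, although protocol 7.4 and SAP 7.4.2.2 allow no dose increase. Under the protocol the switch follows an adverse event, so the distortion falls on participants whose exposure a reader of a safety report would want to see correctly.

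**Working it through.** **Inputs.** The formulas and divisors come from SAP Table 7.4.1-2, the planned schedule from Table 7.4.1-1, and the 4-weekly option from SAP 2.1 and protocol 5.1 and 8.1.2. Body weight is not given; 80 kg is assumed, so that 6 mg/kg equals 480 mg, with 60-100 kg as the range.

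**Check on the planned schedule.** The documents state no numeric RDI to reproduce. With k full cycles the 6 mg/kg term counts k doses and the 480 mg term counts (8(k-1) + 8)/8 = k doses. Expected equals given, so RDI is 100%. The formula is right for the schedule it was written for.

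**Switch without delay.** Let k be the number of combination doses (weeks 0, 8, ..., 8(k-1)) and m the number of 480 mg doses after the last of them, given every 4 weeks from week 8k-4. At 80 kg, in units of 480 mg:

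- given: k + (k-1) + m = 2k - 1 + m
- expected by the SAP: k + [k + (m-1)/2] = 2k + (m-1)/2
- shortfall: (m-1)/2 units, or 240 x (m-1) mg

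With m = 1 there is no error. From m = 2 on, RDI exceeds 100%.

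| Combination doses | Two post-switch doses | Last dose week 48 | Last dose week 52 |
|---|---|---|---|
| 1 | 1440/1200 = 120.0% | 6240/3600 = 173.3% | 6720/3840 = 175.0% |
| 2 | 2400/2160 = 111.1% | 6240/4080 = 152.9% | 6720/4320 = 155.6% |
| 3 | 3360/3120 = 107.7% | 6240/4560 = 136.8% | 6720/4800 = 140.0% |
| 4 | 4320/4080 = 105.9% | 6240/5040 = 123.8% | 6720/5280 = 127.3% |
| 5 | 5280/5040 = 104.8% | 6240/5520 = 113.0% | 6720/5760 = 116.7% |
| 6 | 6240/6000 = 104.0% | 6240/6000 = 104.0% | 6720/6240 = 107.7% |

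After 13 combination doses, two post-switch doses give 12960/12720 = 101.9%. Weight matters little: over 60-100 kg, two post-switch doses after 1-6 combination doses give 103.6-122.2%. At 80 kg the top category is first reached with two post-switch doses after 1-2 combination doses, three after 3-4, and four after 5-6.

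**Switch after a hold.** Protocol 8.1.1 sets the limit: a delay "and >10 weeks for Cohort 1, from the previous dose requires discontinuation", with exceptions. Take a gap of exactly 10 weeks after two combination doses: combination at weeks 0 and 8, 480 mg at week 4, then 480 mg every 4 weeks from week 18 to week 50. That is 12 doses, or 5760 mg at 80 kg. The 6 mg/kg term is 960 mg in every row.

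| Denominator | Expected (mg) | RDI |
|---|---|---|
| SAP formula | 960 + 480 x 54/8 = 4200 | 137.1% |
| Hold charged in full | 960 + 480 x (54/4 - 2) = 6480 | 88.9% |
| 56 days to the first post-switch dose, 28 days from then | 960 + 480 x (14/8 + 36/4) = 6120 | 94.1% |
| Split by segment dates, hold not charged | 960 + 480 x (1 + 9) = 5760 | 100.0% |

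The last three all give 100% when there is no delay; they differ only in how they charge the hold. With just two post-switch doses after the same gap, the SAP formula gives 2400/2520 = 95.2%, against 76.9%, 87.0% and 100% under the same three conventions. With a hold and few later doses, even the direction of the error depends on the convention.

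**The case against.** The strongest defence is that the formula is correct for the planned schedule and that the switch is an optional path needing Medical Monitor approval, taken by an unknown and perhaps small number. That is true and limits the importance, but the SAP itself describes the path and gives no rule for it. Measuring switchers against the planned schedule does not help either, because that schedule also delivers nivolumab every 4 weeks.

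A second defence is that a switch without delay is idealised. Protocol 7.4.1 has delayed participants "resume nivolumab dosing when re-treatment criteria are met", so many switches would follow a hold. This stands as a limit on the percentages after two or more combination doses. After a single combination dose, a delay before the first 480 mg dose does not change the SAP result.

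The IO Core SAP and the Data Presentation Plan were not available and might contain a rule, although SAP 7.4.1 states its own formula without deferring to them for exposure.

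A reader might infer from the 10-week example that a participant who belongs in the 70 to under 90% category is reported at 110% or more. The documents do not support that: they do not say how a hold before a switch is to be charged, and the defensible values run from 89 to 100%, across two categories. Nor may one infer that Cohort 1 exposure is inflated in general. Participants who stay on the alternating schedule are not touched by this mismatch.

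**Conclusion.** The point holds as a minor gap in one descriptive exposure table. For switchers dosed without delay the overstatement is certain once two or more 480 mg doses follow the last combination dose. Its size depends on when combination stopped and how long treatment continued, from about 102% to 175% in the cases computed at 80 kg. After a hold the SAP figure can still be well above any reasonable value, but no single correct value or category can be named. Primary IMAE incidence, dose counts, cumulative dose, the delay summary in SAP 7.4.2.1 and the by-subject dosing listing do not use this denominator and are unaffected. The figures rest on the assumed weights and idealised calendars. No view is taken on which dosing interval is right.

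**What to change.** In the Cohort 1 nivolumab cell of SAP Table 7.4.1-2, add a rule for participants who moved to 480 mg every 4 weeks, identified from the dosing records. Keep the 6 mg/kg term and use a 28-day divisor for the 480 mg doses after the last combination dose. Two forms work:

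- 480 x [(last nivolumab date - first nivolumab date + 28)/28 - (last 6 mg/kg date - first 6 mg/kg date + 56)/56], which charges a hold before the switch in full;
- separate 480 mg terms by segment dates, with 56 days before the switch and 28 days after it, which does not charge that hold.

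Either gives 100% without delay. The SAP should say which hold convention it uses.

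Leave the formula for non-switchers unchanged. Applying the first form to everyone would alter results that this mismatch does not affect: at 80 kg, a non-switcher with six doses and one 4-week hold next to the first or last dose would go from 2880/3120 = 92.3% to 2880/3360 = 85.7% and change category.

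The cost is a derived switch flag and one extra formula line in the SAP and the derivation program. No new data and no change to treatment are needed.

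### SAP Table 7.4.1-2 dates the Cohorts 2-4 nivolumab expected dose from 6 mg/kg doses that these cohorts do not receive, so relative dose intensity is undefined as written

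*SAP*

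**What the plan says.** SAP Section 7.4.1 plans a summary of "Relative dose intensity (%) using the following categories", in five bands from below 50% to 110% and above, for all treated subjects. Table 7.4.1-2 defines RDI as "Cumulative Dose (mg) x100/ Total Expected Dose (mg").

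For nivolumab in Cohorts 2-4, Total Expected Dose is the sum of two terms:

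- **Combination term.** It begins "3 \times \text{Weight}^* \times (\text{Last dose date of } 6\text{mg/kg" and ends "Start dose date of } 6\text{mg/kg} + 21)/21".
- **Maintenance term.** It multiplies 480 mg by the dosing intervals between the first and last 480 mg doses, ending "Start dose date of } 480 \text{ mg} + 28)/28".

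Three other places give the level used in these cohorts:

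- The footnote in the same cell: "Average weight during 3 mg/ kg dosing is used".
- The Duration of Treatment row for the same column: "Last dose date is the last date subject received Nivolumab 3 mg/kg or 480 mg".
- The regimen table, SAP Table 7.4.1-1, Cohorts 2, 3 and 4: "Nivolumab 3 mg/kg Ipilimumab 1 mg/kg Nivolumab 480 mg".

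SAP Section 2.1 and Protocol Section 7.1.2 describe the same regimen. In both documents 6 mg/kg appears only in the Cohort 1 regimen. Protocol Section 7.4 and SAP Section 7.4.2.2 rule out dose escalation.

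**The concern.** The combination term mixes two dose levels. Its multiplier (3), its interval (21 days) and its weight footnote fit the Cohorts 2-4 regimen, but both dates are tied to a level given only in Cohort 1. A program that selects dosing records by the stated level would find none for any Cohorts 2-4 participant treated per protocol.

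This is a derivation rule, not background text. Total Expected Dose is the denominator of nivolumab RDI, so a fault here reaches every RDI value in Cohorts 2-4: about 50 + 25 + 25 = 100 of the 200 participants planned for treatment. SAP Section 7.1 presents summaries by cohort with a total, so the total column would be affected too.

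RDI has some value in this safety trial. Doses may not be reduced, and Protocol Section 7.1 has missed visits postponed rather than omitted, so an RDI below 100% mainly reflects delay. A faulty denominator would hide that for the combination phase.

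**Working it through.** The documents state no RDI value, so there is no planned figure to reproduce. The check applies the formulas to a participant dosed exactly on schedule, whose RDI should be 100%.

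**Inputs.** From the SAP: four combination doses 21 days apart, maintenance 480 mg every 28 days starting 42 days after the last combination dose, and a maximum of 24 months. Assumed, because the documents give no figure: average weight W = 80 kg, with a range of 60 to 100 kg. Let m be the number of maintenance doses. Taking 24 months as 730 days, maintenance starts on day 63 + 42 = 105, and (730 − 105)/28 = 22.3, so at most 1 + 22 = 23 maintenance doses fit.

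**Controls: neighbouring cells, 80 kg, on schedule**

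- Cohort 1 nivolumab, six doses of each kind: expected 6 × 80 × (280 + 56)/56 + 480 × (280 + 56)/56 = 2880 + 2880 = 5760 mg; given 5760 mg; RDI 100%.
- Cohorts 2-4 ipilimumab, four doses: expected 1 × 80 × (63 + 21)/21 = 320 mg; given 320 mg; RDI 100%.

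The table's method is therefore sound where the dates match the regimen.

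**Cohorts 2-4 nivolumab, as written.** There are no 6 mg/kg dates, so the combination term, the expected dose and RDI are all undefined.

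**Same cell, using the 3 mg/kg dates (80 kg, m = 4).** Combination term 3 × 80 × (63 + 21)/21 = 960 mg. Maintenance term 480 × (84 + 28)/28 = 1920 mg. Given 960 + 1920 = 2880 mg. RDI = 2880/2880 = 100%.

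**Same cell, if a program dropped the missing term.** RDI = 100 × (12W + 480m)/(480m).

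| m | Given, 80 kg (mg) | Expected (mg) | RDI, 80 kg | RDI, 60–100 kg |
|---|---|---|---|---|
| 0 | 960 | none | undefined | undefined |
| 1 | 1440 | 480 | 300% | 250–350% |
| 4 | 2880 | 1920 | 150% | 137.5–162.5% |
| 6 | 3840 | 2880 | 133.3% | 125–141.7% |
| 23 | 12000 | 11040 | 108.7% | 106.5–110.9% |

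**Same cell, if a program set the missing date difference to zero.** The combination term becomes one dose, 3 × 80 = 240 mg. With m = 1, RDI = 1440/(240 + 480) = 200%. With m = 4, 2880/2160 = 133.3%. With m = 23, 12000/11280 = 106.4%.

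**Effect on a real delay.** Suppose one 14-day delay in the combination phase, 80 kg, m = 1. With the 3 mg/kg dates the combination term is 240 × (63 + 14 + 21)/21 = 1120 mg, and RDI is 1440/(1120 + 480) = 90.0%. With the term dropped, RDI is 300% whether or not the delay occurred.

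**Participants who stop before maintenance.** Their 480 mg dates are also absent, so correcting the combination dates is not enough. If missing values propagate, RDI stays undefined. If the absent 480 mg difference is set to zero, 480 × 28/28 = 480 mg is added. RDI is then 960/(960 + 480) = 66.7% at 80 kg (60.0% at 60 kg, 71.4% at 100 kg), despite four on-schedule doses.

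**The case against.** The strongest reply is that this is a label slip with one plausible reading. The multiplier, interval, footnote, Duration of Treatment row and regimen table all point to the 3 mg/kg doses, and a careful programmer would use those dates. The formula then works. That stands, and it limits the weight of the point. It does not make the rule correct: a pre-specified derivation should not depend on a silent repair.

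A reader might infer that the plan will report grossly inflated RDI for these cohorts. The documents do not support that. Inflation needs a program that finds no records and then drops the term or sets the difference to zero. No available SAP text prescribes either, and Section 8 refers conventions to a core SAP that is not among the documents. The size also falls with exposure. At 80 kg with 23 maintenance doses, the dropped-term value stays in the 90% to below 110% band, as does the correct value.

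It is also true that a literal failure would be conspicuous (a blank table, or values well above 100% where escalation is barred), and that RDI is descriptive only.

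**Conclusion.** The error is real and confined to one cell. As written, nivolumab RDI cannot be derived for any Cohorts 2-4 participant treated per protocol, about 100 planned. That conclusion rests only on the SAP's own text. The inflation figures are conditional on a default the SAP does not state, and on the assumed weight and on-schedule dosing, so they illustrate and do not predict.

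Not every gap comes from the wrong label. The underivable RDI of participants who stop before maintenance is only partly due to it, because their second term is empty too.

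Number of doses, cumulative dose, ipilimumab RDI, dose delays, duration of treatment, efficacy and the primary endpoint (incidence of high-grade immune-mediated adverse events) do not use this formula. Cohort 1 RDI is untouched by the label error. The point warrants correction but does not threaten the trial's main conclusions. It concerns which dates enter a calculation and takes no position on any dose.

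**What to change.** In the Cohorts 2-4 nivolumab cell of SAP Table 7.4.1-2, reconcile the combination term with Table 7.4.1-1 and the cell's own footnote: 3 × average weight × (last 3 mg/kg dose date − first 3 mg/kg dose date + 21)/21.

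Add one sentence to the table: a term for which the participant received no doses is omitted and contributes 0 mg. It is sensible to apply this to the Cohort 1 nivolumab formula as well, since a participant there who stops before the first 480 mg dose in Week 5 leaves its second term empty in the same way.

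The cost is a wording correction and a matching check of the exposure program. No new data are needed, and no other analysis changes.
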